**Effects of a health education intervention based
on the behaviour change wheel on fear of
hypoglycemia in patients with type 2 diabetes
mellitus: a pilot study**

January 14, 2021

Study Protocol

1. Integrity Statement

(1) Ensure that the operation is in strict accordance with the test protocol and the authenticity of the data records; (2) No conflict of interest with other projects.

2. Title of the study

Effects of a health education intervention based on the behaviour change wheel on fear of hypoglycemia in patients with type 2 diabetes mellitus: a pilot study

3. Flow chart of the implementation of the study

Specific implementation elements of the Intervention programme

| Behavioural analysis with the BCW theory | | Intervention function | Specific interventions | Implementation modalities | Implementation time |
|--|--|--|--|---|--|
| Motivations | Spontaneous motivation Intensive daily diabetes management to change attitudes and habits. | Education, training, persuasion, modelling | 1. Fill in the hypoglycaemia fear scale on the first day of admission, grasp the obstacles in blood glucose management and hypoglycaemia cognition, correct the wrong cognition on a one-to-one basis, and establish the scientific concept of blood glucose management. | Questionnaires, face-to-face interviews | Day 1 of admission, duration 15min |
| | | | 2. Introduce the knowledge of diabetes, hypoglycaemia and fear of hypoglycaemia to patients through PPT teaching. | PPT lectures and video learning | Days 2, 4 and 6 of admission, each 60 min long |
| | | | 3. 1-3 weeks after discharge, describe blood glucose management management and how to respond when hypoglycaemia occurs through patient diaries. Encourage patients to upload and share their hypoglycaemic fear and diet and exercise diaries in WeChat group, and patients with good psychological status to share their feelings. | WeChat or telephone communication | Weeks 1, 2 and 3 after discharge, 1 time per week, 15min each time |
| | | | 1. Personalised guidance on knowledge about hypoglycaemia was pushed through WeChat to reshape, as far as possible, their sense of self-efficacy in relation to glycaemic control. | WeChat | Every Monday of the 1st, 2nd and 3rd week after discharge |
| | | | 2. Use examples to illustrate the dangers of excessive avoidance behaviours caused by the fear of hypoglycaemia. | WeChat | 60min on the 6th day of admission |
| | Introspective motivation Understand the negative consequences of fear of hypoglycaemia, improve hypoglycaemia awareness and self-regulation skills, set blood glucose control goals to maintain stable blood glucose and reduce the occurrence of abnormal blood glucose. | | 3. Encourage patients with stable glycaemic management to share their experiences and set an example for other patients. | WeChat or telephone communication | Every 3rd week after discharge 15min duration |

(Continued)

| Behavioural analysis with the BCW theory | | Intervention function | Specific interventions | Implementation modalities | Implementation time |
|--|---|---|--|---|--|
| Capability | Mental capacity Raise awareness of hypoglycaemia, detect hypoglycaemia in a timely manner, acquire scientific knowledge about hypoglycaemia, and understand the health problems associated with the fear of hypoglycaemia. | Education, training, realisation | 1. Fill in the questionnaire on the first day of admission to understand the patient's psychological state and knowledge of hypoglycaemia fear. | Questionnaire | Day 1 of admission, duration 15min |
| | | | 2. Introduce patients to diabetes mellitus as well as knowledge about hypoglycaemia and hypoglycaemia fear and the impact it has on diabetes mellitus. | Interpretation of the Type 2 Diabetes Hypoglycaemia Health Education Manual | Day 1 of admission, duration 15min |
| | | | 3. Help patients to look for clues to the occurrence of hypoglycaemia and the causes and consequences of impaired awareness of hypoglycaemia, and instruct patients on how to reduce hypoglycaemia exposure. | Face-to-face Interview | Day 1 of admission, duration 15min |
| | | | 4. Re-completion of the questionnaire to understand the patient's knowledge of hypoglycaemia and fear of hypoglycaemia | Questionnaire Survey | Day 1 before discharge, duration 15min |
| | Physical capability In the event of a hypoglycaemic event, patients know how to deal with it, how to monitor their blood glucose appropriately and how to calculate the amount of diet and exercise to maintain a stable blood glucose level. | | 1. Introduce patients to proper diet, moderate exercise and rational use of medication, the correct way of monitoring blood glucose, identifying the pre-symptoms of hypoglycaemia, and how to deal with them. | PPT lectures and video learning | Days 2, 4 and 6 of admission, each lasting 60 min. |

(Continued)

| Behavioural analysis with the BCW theory | | Intervention function | Specific interventions | Implementation modalities | Implementation time |
|--|---|--|--|---|-------------------------------|
| Opportunity | Social opportunities The external environment and medical support are facilitators of change in patients' hypoglycaemic fear-avoidance behaviour, and reasonable and effective diabetes support is provided with due consideration of external factors and their own opportunities. | Environmental reconstruction, realisation | 1. Develop an individualised self-management plan based on the patient's glycaemic control, and commit the patient to follow this plan for self-management. | Face-to-face interviews | Day 1 before discharge, 15min |
| | 2. Instruct the patient's family members to control their diet and behaviour, provide family support and play a good role in supervision and care. | | Face-to-face interviews | Day 1 before discharge, 15min | |
| | 3. Discharged patients can join the WeChat group to push diabetes-related counselling. | | Wechat | Every Monday of the 1st, 2nd and 3rd weeks after discharge | |
| | 4. Regular nursing visits to the patients, recalling the recent life with the patients, finding out whether the patients have hypoglycemia and analysing the causes of hypoglycemia. | | WeChat or telephone communication | Weeks 1, 2 and 3 after discharge, 1 time per week, duration 15min | |
| | Physical opportunity Glucose management through WeChat platform, on-site teaching and guidance by specialist nurses to create opportunities for patients who can change excessive/avoidant behaviours. | | 1. Specialist nurses on-site instructed patients on how to correctly monitor blood glucose, how to calculate daily diet and exercise, and how to correctly deal with abnormal blood glucose. 2. Through the WeChat group peer communication, exchange insights and tips with patients who have ideal blood glucose control on-site, through the exchange of knowledge and provide assistance. | On-site Teaching WeChat communication Questionnaire | Practical group |

4. Background

Fear of hypoglycemia (FoH) is becoming an important barrier to achieving good glycemic control in patients with type 2 diabetes. Clinical care professionals have been working to address FoH in patients with diabetes mellitus, and the behaviour change wheel (BCW) theory, which states that individuals must possess the three behavioral components of ability, opportunity, and motivation in order to develop behavioral change, helps interventionists analyze the behavioral components that are lacking in order to determine the focus of the intervention, and then select the most appropriate intervention based on the combination of the nine functions of the intervention and implement it. The purpose of this study was to develop a health education intervention program based on the BCW theory to reduce the level of fear of hypoglycemia in patients with type 2 diabetes and to investigate the feasibility, acceptability, and preliminary effects of the program.

5. Research purpose

The purpose of this study was to develop a health education intervention program based on the BCW theory to reduce the level of fear of hypoglycemia in patients with type 2 diabetes and to investigate the feasibility, acceptability, and preliminary effects of the program.

6. Inclusion and Exclusion Criteria

Inclusion criteria: (1) Compliance with the 2020 Chinese guidelines for the prevention and treatment of type 2 diabetes mellitus patients^[24]; (2) Age ≥ 18 years; (3) Duration of diabetes mellitus ≥ 1 year; (4) According to the elevated item endorsement criterion (EI criterion): Hypoglycaemic Fear-Worry Scale (HFS-WS) Any item ≥ 3 points was judged as FoH; (5) Have the ability to listen, read, write and walk, and be able to cooperate with the completion of the study; (6) Have a smart phone, and be able to use WeChat or phone to communicate proficiently; (7) Voluntarily participate in this study and sign the informed consent form. Exclusion Criteria: (1) Those who are combined with acute complications or other serious diseases or disorders of consciousness, such as diabetic hypertonic state, tumour, coma, etc.; (2) Those who are combined with psychiatric diseases or taking psychotropic drugs. (3) Patients who have recently or are

participating in other studies on similar topics.

7. Intervention process

From August 2021 to January 2022, T2DM patients who met the inclusion and exclusion criteria were selected from 2 tertiary hospitals in Yangzhou City. The control group implemented conventional diabetes health education, and the intervention group implemented health education based on BCW theory on top of the control group.

8. Sample size estimation

According to the formula for calculating the sample content: $n_1=n_2=2[(Z_{\alpha}+Z_{\beta}) \sigma/\delta]^2$, n_1 , n_2 are the required sample contents of the two groups, set $\alpha=0.05$, $\beta=0.1$, check the boundary table $Z_{\alpha/2}=1.96$, $Z_{\beta}=1.282$. $n_1=n_2 \approx 22$ cases according to the sample size estimation formula of the pre-experimental results substituted into the comparison of the two sample means, considering a 15% attrition rate, expert opinion and clinical situation, 25 patients in each group were finally determined.

9. Randomisation

Participants were identified through screening of medical records and face-to-face interviews, and participants signed a written consent form to participate in the study. After the baseline assessment, participants were randomly assigned to either the intervention or control group using a lottery method after drawing a labelled card in an opaque sealed envelope from an independent research assistant who was not involved in the recruitment and implementation of the study.

10. Measurement index

General information questionnaire: admission day 1; hypoglycaemia fear scale (primary indicator): admission day 1, 4 weeks post intervention, 8 weeks post intervention; impaired hypoglycaemia awareness score (secondary indicator): admission day 1, 4 weeks post intervention, 8 weeks post intervention; medical support scale (secondary indicator): admission day 1, 4 weeks post intervention, 8 weeks post intervention; diabetes self-management attitude scale (secondary indicator). Day 1 of admission, 4 weeks post-intervention, 8 weeks post-intervention.

11. Ethical consideration

The study was ethically approved by the Ethics Committee of the College of Nursing

of Yangzhou University (YZUHL20210088).

12. Statistical analysis of data

SPSS 26.0 software was applied for data analysis. Describing the general demographic characteristics of the study population: Mean \pm standard deviation ($\pm s$) was used to describe measures that conformed to normal distribution, and median and interquartile spacing M (QR) were used to describe skewed distribution; count data were expressed as frequencies and constitutive ratios. Homogeneity test: the chi-square test or Fisher's exact test was used for the count data of the two groups at baseline, non-parametric test was used for the rank count data, and t-test or non-parametric test was used for the measurement data. Repeated measures ANOVA was used to analyse the intervention effect of each indicator within groups, and two independent samples t-test was used to compare between groups at different time points before and after the intervention. The significance level $P < 0.05$ indicated that the difference was statistically significant.

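### Enrolling 25 per group is about one patient per group short of what 22 evaluable with 15% attrition requires, so power at that attrition is slightly below the stated 90%

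*Combined protocol and SAP*

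**What the plan says.** Section 8 uses the standard formula for two means, n per group = 2[(Z_alpha + Z_beta) x sigma/delta]^2, with alpha 0.05 and beta 0.1. The values entered are 1.96 (so the test is two-sided) and 1.282. The result, about 22 per group, is said to come from the "sample size estimation formula of the pre-experimental results substituted into the comparison of the two sample means". Neither delta nor sigma is given.

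The step from 22 to the final size is one clause: "considering a 15% attrition rate, expert opinion and clinical situation, 25 patients in each group were finally determined". No inflation formula is shown.

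Section 12 (Statistical analysis of data) gives the between-group analysis: "two independent samples t-test was used to compare between groups at different time points before and after the intervention". The title calls the trial a pilot, and Section 5 (Research purpose) names feasibility, acceptability and preliminary effects.

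**The concern.** Section 8 puts four figures together: 22 needed, beta 0.1, 15% attrition, 25 enrolled. Read in sequence, they imply that 25 per group still leaves enough evaluable patients for 90% power after 15% are lost. The usual inflation of 22 for 15% loss gives more than 25, so either the attrition allowance or the power is slightly overstated.

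What is at stake is the accuracy of a stated design property. The plan justifies its size by power and declares significance at P < 0.05, so a reader will rely on the 90%. No change in the number of patients hangs on it.

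**Working it through.** **Inputs from Section 8:** n of about 22 per group; 1.96 and 1.282 (sum 3.242); attrition 15%; 25 enrolled per group. **From Section 12:** independent-samples t-test. **Assumed:** delta/sigma, because the plan does not report it.

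**Step 1. The plan's own figures.** The 22 cannot be recomputed without delta and sigma. The 25 can be approached in two ways:
- Dividing by retention: 22/(1 - 0.15) = 25.88, so 26.
- Multiplying by 1.15: 22 x 1.15 = 25.3, which is 26 rounded up and 25 only if rounded to nearest.

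**Step 2. What 25 provides.** 25 x 0.85 = 21.25, so about 21 evaluable per group. The attrition that 25 can bear while keeping 22 is 1 - 22/25 = 0.12. In whole patients, losing 3 of 25 leaves 22, and losing 4 (16%) leaves 21. By comparison, 26 x 0.85 = 22.1.

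**Step 3. Implied effect.** Inverting the plan's formula, delta/sigma = 3.242 x sqrt(2/22) = 0.9775. Since 22 is printed as approximate, the unrounded value could lie between just over 21 (rounded up) and just under 22.5 (rounded to nearest). That gives delta/sigma from about 1.00 down to 0.97.

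**Step 4. Power with m evaluable per group.**
- Normal approximation (the plan's formula): Phi(delta/sigma x sqrt(m/2) - 1.96). For m = 21: 0.9775 x sqrt(10.5) - 1.96 = 1.207, so power is 88.6%.
- Two-sided t-test: noncentral t with 2m - 2 degrees of freedom and noncentrality delta/sigma x sqrt(m/2). For m = 21: 87.1%.

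| Unrounded n behind 22 | delta/sigma | Normal, m = 21 | Normal, m = 21.25 | t-test, m = 21 | t-test, m = 21.25 |
|---|---|---|---|---|---|
| 21.01 | 1.0003 | 90.0% | 90.3% | 88.5% | 88.9% |
| 21.5 | 0.9888 | 89.3% | 89.7% | 87.8% | 88.2% |
| 22 | 0.9775 | 88.6% | 89.0% | 87.1% | 87.5% |
| 22.49 | 0.9668 | 88.0% | 88.3% | 86.4% | 86.8% |

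**Step 5. Splitting the t-test gap.** With delta/sigma = 0.9775 and all 22 evaluable, t-test power is already 88.6%, not 90%. So 90.0 - 88.6 = 1.4 points come from sizing a t-test with the normal formula, and 88.6 - 87.1 = 1.5 points come from going from 22 to 21 patients. With no attrition at all, 25 per group gives 92.3% by t-test at the same effect.

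**The case against.** A reader might infer that 25 per group cannot absorb the stated attrition and that 90% power is simply not delivered. The documents do not support that. The 22 is a rounded figure with no delta or sigma behind it. If the unrounded value was between 21 and 21.25, then 21.25/0.85 = 25, and 25 per group meets 15% attrition exactly by the plan's own formula. This stands: by that formula, a loss of power cannot be established. It does not carry over to the planned t-test, whose power at about 21 evaluable stays below 90% at every value in the table.

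A second objection is that the plan never says 25 is 22 inflated for attrition alone, since expert opinion and the clinical situation were also weighed. That may well explain the choice of 25. It does not make 25 provide both 15% attrition and beta 0.1 from a base of 22.

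Third, using the normal formula to size a t-test is common practice, and the plan shows the formula openly. That is fair, and it is why the full drop from 90% to 87% should not be attributed to attrition.

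Finally, this is a pilot, and one patient per group around an unreported effect changes no decision. That supports treating the point as minor. It does not remove the case for correcting a stated figure when the correction costs nothing.

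**Conclusion.** The point holds as a small inconsistency. From a base of 22, 15% attrition calls for 26 per group; the stated 25 leaves about 21 and matches an allowance of 12%. The shortfall is one patient per group.

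At 15% attrition, power is about 89% by the plan's formula (88% to 90%) and about 87% by the planned t-test (86% to 89%), against a stated 90%. These power figures rest on a delta/sigma of about 0.98 recovered from n = 22, with 0.97 to 1.00 covering the rounding. They also assume a single two-sided comparison at 0.05 and equal losses in the two groups. The enrolment arithmetic needs only the printed 22, 15% and 25.

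The missing delta and sigma, and the formula's Z_alpha where the two-sided value 1.96 is used, are a reporting gap and a clerical matter. Neither shows that the sample size is wrong.

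**What to change.** Keep 25 per group and revise the last sentence of Section 8 to say two things:
- 25 per group allows for 12% attrition (3 of 25) while keeping 22 evaluable.
- At 15% attrition, with 21 evaluable per group, the power of the two-sided t-test at alpha 0.05 is the value recomputed from the delta and sigma observed in the pre-experiment.

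The sponsor should enter its own delta and sigma here, not the 0.98 used above. That ratio is only a back-calculation, and printing it beside different true inputs would create a new discrepancy. If practical limits fixed the number at 25, the text can say so.

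The change is to text only and adds no patients. Its one downside is that the stated power becomes slightly less favourable than 90%.

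### Hospital appears in neither the described randomisation nor the between-group analysis of a two-hospital trial, which costs precision and leaves an unlucky draw uncorrected

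*Combined protocol and SAP*

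**What the plan says.** Section 7 states that patients "were selected from 2 tertiary hospitals in Yangzhou City". On the comparator it says "The control group implemented conventional diabetes health education", without saying whether that education is the same in both hospitals.

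Section 9 says participants were "randomly assigned to either the intervention or control group using a lottery method after drawing a labelled card", the card being "in an opaque sealed envelope from an independent research assistant who was not involved in the recruitment and implementation of the study". Concealment and independence of the allocator are therefore addressed. Stratification, blocking, the number of cards, and whether there was one draw or one per hospital are not.

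Section 12 gives two analyses of effect. Change over time inside each arm is assessed by a repeated measures ANOVA. For the comparison of the arms, the plan reads: "two independent samples t-test was used to compare between groups at different time points before and after the intervention". Neither contains hospital. The baseline homogeneity tests ("the chi-square test or Fisher's exact test was used for the count data of the two groups at baseline") do not name hospital as a variable.

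Section 8 sets two-sided alpha 0.05 and 90% power, arrives at about 22 per group, and fixes 25 per group, 50 in all.

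**The concern.** Hospital is known for every patient before randomisation and may carry outcome differences. The intervention is delivered by staff, with on-site teaching by specialist nurses and sessions tied to days of the admission, and one secondary outcome is a medical support scale. If the two hospitals do differ, no step of the plan balances them across arms, shows whether they are balanced, or removes the difference from the comparison. Between-hospital variation then stays in the error term of the t-test. If the one draw obtained happens to be uneven, part of the hospital difference sits inside the estimated treatment effect. At stake are the precision and interpretability of the preliminary effect on the fear scale.

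**Working it through.** **Inputs from the documents.** Two hospitals (Section 7); 25 per group, Z values 1.96 and 1.282, about 22 per group before attrition (Section 8); unadjusted t-tests (Section 12). **Assumed, because the documents are silent:** the hospital split (25/25, 35/15 or 40/10) and the hospital effect (0 to 1.0 SD, in units of the within-hospital SD). All 50 patients are taken as analysed.

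**1. The plan's own figure.** The 22 cannot be reproduced forwards, because neither the difference nor the SD is given. Solved backwards, n = 2[(1.96 + 1.282)/d]² = 22 gives d = √(2 × 3.242²/22) = 0.98 SD. With 25 per group and no hospital effect, the t-test has 92.3% power at that d.

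**2. Chance of imbalance.** Take a lottery with 25 cards per arm, not stratified by hospital. If hospital A supplies s of the 50 patients and x of them fall in the intervention arm, x is hypergeometric (50, s, 25). The gap in hospital share between arms is |2x − s|/25.

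| Hospital split | Gap of at least 20 points | Gap of at least 28 points |
|---|---|---|
| 25/25 | 26% | 9% |
| 35/15 | 22% | 6% |
| 40/10 | 7% | 1% |

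For 25/25, a 20-point gap is a 15:10 split of one hospital (|30 − 25|/25 = 0.20). For 40/10 only even values of |2x − s| occur, so the smallest gaps that qualify are 24 points (6/25) and 32 points (8/25).

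**3. Shift in the estimate, given the draw.** Shift = gap × hospital difference.
- 0.20 × 0.5 SD = 0.10 SD
- 0.28 × 1.0 SD = 0.28 SD

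The standard error of the difference is √(2/25) = 0.28 SD, so these are about one third of a standard error and one standard error. Against the 0.98 SD design effect they are about 10% and 29%.

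**4. Error rate and power.** Simulation, 40,000 trials per scenario, 25/25 split. The last two columns are at a true effect of 0.98 SD.

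| Hospital effect | Type I error, t-test, all draws | Type I error, t-test, gap ≥ 20 points | Type I error, t-test, gap ≥ 28 points | Power, planned test | Power, stratified and adjusted |
|---|---|---|---|---|---|
| 0.25 SD | 4.9% | 5.2% | 5.6% | 91.9% | 92.1% |
| 0.5 SD | 5.1% | 6.4% | 7.2% | 90.7% | 92.4% |
| 0.8 SD | 5.1% | 8.1% | 11.1% | 88.0% | 92.3% |
| 1.0 SD | 5.1% | 9.5% | 13.7% | 85.6% | 92.2% |

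With hospital in the model, type I error is about 5% both over all draws and in draws with a gap of at least 20 points. The power differences run from 92.1 − 91.9 = 0.2 points to 92.2 − 85.6 = 6.6 points. Adjustment alone, without stratification, gives 91.7 to 91.8% throughout, so most of the gain comes from the model.

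**The case against.** The strongest reply is that simple randomisation with concealed envelopes and an independent allocator is a valid choice in a pilot of 50. Chance imbalance by hospital is already inside the 5% error rate. That stands, and the all-draws column above shows it. A reader might infer that the plan biases the treatment effect or inflates type I error; neither is true averaged over draws. The raised rates apply only conditionally on a poor draw.

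A reader might also infer one common lottery, or that each hospital gives its own form of conventional education. Section 9 does not say how the draw was organised across hospitals, and Section 7 does not say that the education differs. Nor do the documents support calling hospital the leading prognostic factor: the baseline fear score is a stronger candidate, and adjusting for it would absorb any hospital difference already present at admission.

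Overall group sizes are not a serious worry. Section 8 fixes 25 per group, and even 29:21 would keep 4 × 29 × 21/50² = 97.4% of the efficiency.

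Finally, a t-test has no place for a hospital term, so the analysis method must change and not merely gain a word. That is correct and is carried into the fix. It does not remove the point, because the plan tests effects at P < 0.05 and was sized for 90% power.

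**Conclusion.** The point holds as one of precision and reporting. Hospital is absent from the described allocation and from the planned comparison. If the hospitals do not differ, nothing of substance is lost. If they differ by 0.5 SD, the planned test loses 1 to 2 power points; at 1.0 SD it loses about 7. An imbalance of 20 points or more is plausible (7 to 26% across the splits considered), but the resulting shift is modest against 0.98 SD unless the hospitals differ strongly. These figures rest on assumed hospital splits and hospital effects, an unstratified draw with 25 cards per arm, and a design effect recovered from n = 22. If the lottery was in fact run per hospital with balanced cards, the imbalance figures fall away and only the omission from the analysis remains. The change is a cheap improvement, not the repair of an invalid test.

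**What to change.** - In Section 12, replace the between-group t-test on the hypoglycaemia fear scale with a linear model containing arm and hospital as fixed factors.
- Tabulate hospital by arm with the baseline characteristics.
- In Section 9, state whether the lottery was central or per hospital and how the cards were prepared.
- If enrolment has not started, prepare a separate blocked set of sealed envelopes for each hospital, held by the same independent assistant.

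The cost is one degree of freedom (47 residual instead of 48), a change of analysis method in Section 12, and a second envelope set. The sample size stays at 50. If enrolment is under way, the model, the table and the clarification of Section 9 can still be adopted.

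### The primary fear scale is tested between groups at both 4 and 8 weeks, each at P<0.05, and the plan does not say which test decides the primary result

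*Combined protocol and SAP*

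**What the plan says.** - **Section 8 (sample size).** The calculation uses the formula for "the comparison of the two sample means", with "set $\alpha=0.05$, $\beta=0.1" and critical values "Z_{\alpha/2}=1.96$, $Z_{\beta}=1.282". The value 1.96 makes the test two-sided. The result is about 22 per group, and after an allowance for 15% attrition and other considerations "25 patients in each group were finally determined". No time point is attached to the comparison.
- **Section 10 (measurement index).** The fear scale appears as "hypoglycaemia fear scale (primary indicator): admission day 1, 4 weeks post intervention, 8 weeks post intervention". Neither follow-up is marked as primary. Three further scales, all labelled secondary, follow the same schedule.
- **Section 12 (analysis).** For group comparisons, "two independent samples t-test was used to compare between groups at different time points before and after the intervention". Repeated measures ANOVA is also planned, but only for change within groups. One rule covers every test: P below 0.05 "indicated that the difference was statistically significant". No primary test, testing order, multiplicity adjustment or exploratory label is given.
- **Title and Section 5 (purpose).** The study is called a pilot, and its aims are feasibility, acceptability and preliminary effects.

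**The concern.** The design allows for one between-group test on the primary outcome, and the analysis delivers two, each at the full 0.05. The repeated measures ANOVA does not close the gap: as described it works inside each group, so no overall group comparison or group-by-time test stands in front of the two t-tests.

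With no deciding test named, the sponsor could report whichever of 4 or 8 weeks came out significant as the primary finding, and a reader could not tell whether that choice was made before or after the results were seen. What is at stake is the error rate attached to the trial's main statement about fear of hypoglycaemia.

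**Working it through.** **1. The plan's own figure.** Section 8 uses n per group = 2[(Z_alpha + Z_beta) × sigma/delta]², with 1.96 for two-sided alpha 0.05 and 1.282 for 90% power. Both critical values are correct. The 22 itself cannot be reproduced, because sigma and delta come from pre-experimental results that the plan does not report. Solving backwards:

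delta/sigma = (1.96 + 1.282) × √(2/22) = 3.242 × 0.3015 = 0.977

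So 22 per group corresponds to one two-sided test at 0.05 with 90% power for a standardised difference of about 0.98. There is no allowance for a second primary test. (22/0.85 = 25.9, which rounds up to 26; the stated 25 is close and does not affect this point.)

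**2. Tests on the primary scale.** After baseline there are two between-group t-tests, at 4 and at 8 weeks, each at 0.05.

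**3. False-positive rate if either test can carry the claim.** With no true effect at either time:

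- Independent tests: 1 − 0.95² = 0.0975.
- Correlated tests: 1 − P(|Z1| < 1.96 and |Z2| < 1.96), where Z1 and Z2 are bivariate normal with correlation r, the within-group correlation between the 4- and 8-week scores. The documents give no r, so a range is shown.

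| Assumed r | Chance of at least one P<0.05 |
|---|---|
| 0 | 0.0975 |
| 0.5 | 0.091 |
| 0.7 | 0.083 |
| 0.9 | 0.070 |

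The rate is above 0.05 for every r below 1.

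**4. Remedies.**

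- *One named follow-up at 0.05.* The error rate on the primary claim is 0.05 and the calculation of 22 per group is unchanged. Testing the other follow-up at 0.05 only after the first succeeds adds no error.
- *Either follow-up may succeed.* Bonferroni at 0.025 each gives 1 − 0.975² = 0.0494 if the tests are independent, and never more than 0.05. Holm starts at the same level. At the back-solved effect of 0.977 and 22 per group, normal-approximation power for a single test falls from 90% to 84.1%. To restore 90% per test, n = 2[(2.241 + 1.282)/0.977]² ≈ 26 per group, and 26/0.85 = 30.6, so 31 enrolled.
- That per-test figure is not the chance of success under Holm, which needs only one of the two to be significant. With t-tests, 21 per group (25 × 0.85 = 21.25) and the same effect of 0.9775 at both times, simulation gives a chance of at least one rejection of about 91%, 88–89% and 85% at r = 0.5, 0.7 and 0.9. A single t-test at 0.05 has 87%.

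**The case against.** **This is a pilot.** Strict control of the error rate matters most when one test settles a confirmatory question, and this study seeks preliminary effects. That stands as a reason for lower severity. It does not remove the point: the plan names a primary indicator, sizes for 90% power at alpha 0.05, declares significance at P<0.05 and nowhere calls its tests exploratory.

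**The inflation depends on how success is read.** If both follow-ups had to be significant, the error rate would not rise. This is correct, so a flat statement that alpha is exceeded would go too far. The plan is silent on the rule, and the supportable statement is that 0.05 is not guaranteed.

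**The error may be well short of double.** Scores on one scale four weeks apart could correlate strongly; at r = 0.9 the rate is 7.0%, about 1.4 times nominal. This also stands. Nearly double describes only the low-correlation end.

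**The secondary scales.** A reader might add the three secondary scales, count eight follow-up tests, and quote 1 − 0.95⁸ = 0.337 (roughly 0.21 to 0.30 under assumed correlations of 0.5 to 0.9 between times and 0.3 to 0.5 between scales). The documents do not support using that figure for the primary claim. Section 10 separates one primary indicator from three secondary ones, and tests on the latter do not raise the error on the former. The eight-test figure would matter only if any significant scale counted as trial success, and the plan contains no such rule.

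**Conclusion.** The point holds for the primary scale. One comparison is planned at two-sided 0.05, two are carried out at that level, and nothing says which decides. On an either-time reading, which the plan leaves open, the false-positive rate for the primary claim is about 7.0% to 9.75%. This rests on an assumed correlation between follow-ups of 0.9 to 0 and on the usual normal approximation.

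Two further inferences should be resisted. The documents do not favour 8 weeks over 4 weeks as the primary time, so neither can be called the intended one. Nor does protecting the primary claim require a ban on significance tests for the secondary scales.

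Severity: should be fixed. The gap bears on the main conclusion and is cheap to close, but the pilot aim keeps it below an essential correction.

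**What to change.** Amend Sections 10 and 12 before outcome data are examined:

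1. Name one primary between-group test of the fear-scale score at two-sided 0.05. It may be the difference at one follow-up, chosen by the sponsor, or one overall between-group test across both follow-ups.
2. If one follow-up is primary, test the other only when the first is significant. If success at either time is wanted, apply Holm to the two instead.
3. State that the within-group repeated measures ANOVA and the tests on the secondary scales are supportive and cannot by themselves establish the primary effect. Without this, a within-group P<0.05 remains another route to a positive claim.

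No date of unblinding can serve as the deadline, because the plan describes concealed allocation but no blinding; the deadline should be the first look at outcome data.

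**Cost.** A few sentences. With one follow-up named, no extra patients are needed and the 22-per-group calculation carries over, provided the pre-experimental sigma and delta apply to that time point, which Section 8 should then say. The downside is that an isolated P<0.05 at the non-primary follow-up can no longer be called a positive primary result. Holm avoids that, at the price of a stricter first threshold of 0.025.
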